**Table 1. Schedule of Assessments**

	30-day Screening	Open-Label Run-in Period h				Double Blind Treatment Period g						Follow-Up
Weeks		Run-in Visit 1	Run-in visit 2	Run-in visit 3	Run-in ET	0 g	12	24	36	48/ET	Disease Assessment e	Safety (EOS) i
Days	-198 (from Day 1)	-168 (from Day 1)	-84 (from Day 1)	-7 (from Day 1)		Day 1						30
DOSING												
Etanercept/placebo for etanercept dispensation		X	X			X	X	X	X		X f	
Methotrexate/placebo for methotrexate dispensation		X	X			X	X	X	X		X f	
Dispense dosing diary		X	X			X	X	X	X			
Review dosing diary			X	X	X	X	X	X	X	X	X	
DISEASE ASSESSMENTS												
66 Swollen joint count	X	X	X	X		X	X	X	X	X	X	
68 Tender joint count	X	X	X	X		X	X	X	X	X	X	
Physician global assessment of disease activity	X	X	X	X		X	X	X	X	X	X	
SUBJECT ASSESSMENTS (PRO)												
Patient global assessment of joint pain	X	X	X	X		X	X	X	X	X	X	
Patient global assessment of disease activity	X	X	X	X		X	X	X	X	X	X	
Disability Index of the Health Assessment Questionnaire (HAQ-DI)						X		X		X		
Medical Outcomes Short Form-36 Questionnaire (SF-36)						X		X		X		

ET = early termination; ESR = erythrocyte sedimentation rate; EOS = end of study; HBV = hepatitis B virus; PCR = polymerase chain reaction.

a Screening physical exam will be a full exam; subsequent exams per standard of care to monitor for any changes

b For all women, unless at least 2 years postmenopausal or history of hysterectomy, bilateral salpingectomy, or bilateral oophorectomy

c Additional pregnancy testing may be completed at the discretion of the investigator

d Subjects will receive either a PPD test or Quantiferon test at screening. National guidelines should be followed for appropriate tuberculosis screening in the setting of anti-TNF therapy.

e Disease Assessment Visit - disease activity may be assessed at a regularly scheduled visit or at a Disease Assessment visit as described in [Section 7.2.7](#)

f If subjects meet the criteria for disease worsening then etanercept plus methotrexate will be dispensed at the same dose they were receiving at screening

g Baseline (Day 1) visit must be scheduled ≤7 days from the run-in visit 3

h Visit window is +/- 7 days for all visits after screening

i Subjects will be contacted by phone by the site staff to collect any serious adverse events

j At screening, if the subject is positive for hepatitis B core antibody, the confirmatory reflex testing will be performed using HBV DNA PCR.

## 7.2 General Study Procedures

The procedures performed at each study visit are outlined in [Table 1](#). Details regarding each type of procedure are provided in subsequent sub-sections.

Refer to the applicable supplemental central laboratory, IXRS, IPIM, and study manuals for detailed collection and handling procedures.

### 7.2.1 Screening

Informed consent must be obtained before completing any other screening procedure. After written informed consent is signed by the subject, the subject will be screened in order to assess eligibility for study participation. The screening window is 30 days. If a subject has not met all Part 1 eligibility criteria at the end of the 30-day window, the subject will be registered as a screen fail. At screening, if the subject is positive for hepatitis B core antibody, the confirmatory reflex testing will be performed using hepatitis B virus (HBV) DNA polymerase chain reaction (PCR). Subjects who screen fail may be eligible to rescreen two additional times per [Section 7.2.2](#).

### 7.2.2 Re-screening

Subjects who are unable to complete or meet Part 1 eligibility criteria on initial screening will be permitted to re-screen two additional times after the first screening visit failure. Re-screen subjects must first be registered as screen failed in IXRS and subsequently registered as a re-screen subject with the same subject identification number. Once the subject is registered as re-screened, a new 30-day screening window will begin.

If the re-screening period begins more than 30 days after the original signing of the informed consent form, all screening procedures, including informed consent must be repeated. If the re-screening occurs within 30 days after the original signing of the informed consent, only those criteria that were originally not met would be required to be repeated. Tuberculosis testing will not need to be repeated for re-screen subjects if negative at the original screening. Subjects who fail screening for not meeting inclusion criterion 114 are not permitted to re-screen. Subjects screen failing for not meeting inclusion criteria 106 are permitted to re-screen 1 additional time if their initial SDAI screening score is < 6.0. If a subject does not meet inclusion criteria 106 after 2 screening attempts no additional rescreening is permitted. Rescreening for failure to meet inclusion criteria 106 must occur at least 2 weeks after the initial screening.

### **7.2.3 Open Label Run-in Period**

Once a subject has met the Part 1 eligibility criteria evaluated during screening, the subject will enter the 24-week open-label run-in period. During the run-in period, Part 2 eligibility criteria will be evaluated at the regularly scheduled run-in visits or at a Disease Assessment visit (see [Section 7.2.7](#)) if required. If the subject does not meet the Part 2 eligibility criteria they must complete a run-in early termination visit.

Subjects will initiate treatment with open-label etanercept and methotrexate at the same dose they were receiving at screening. Investigational products, subject diaries, and related supplies will be dispensed to the subject at every regularly scheduled visit for self-administration.

All procedures during run-in visit 3 (see [Table 1](#)) must be completed within 7 days of the baseline (day 1) visit in order to confirm the subject's eligibility.

### **7.2.4 Early Termination Run-in**

Subjects not meeting Part 2 eligibility criteria will complete a run-in early termination visit and will complete the procedures described in [Table 1](#).

### **7.2.5 Baseline Visit (Day 1)**

Subjects meeting Part 1 and Part 2 eligibility criteria will be randomized by IXRS as described in [Section 5](#). The date of first dose of blinded investigational product is defined as Day 1 Week 0. All subsequent doses and study visits will be scheduled based on the Day 1 date. Following the first blinded dose, investigational products and related supplies will be dispensed to the subject for 12 weeks of self-administration.

### **7.2.6 Treatment**

Visits will occur per the Schedule of Assessments ([Table 1](#)) during the treatment period from day 1 until week 48. On-study visits may be completed within  $\pm 7$  days of the target visit date. The procedures completed during the 48-week treatment period are those listed in the Schedule of Assessments ([Table 1](#)). Administration of investigational product is to be administered after all other study procedures, as applicable, during each visit that is required.

### **7.2.7 Disease Assessment Visit**

Subjects can be seen at a regularly scheduled visit or at a disease assessment visit any time after screening to assess disease activity to either:

- establish Part 2 eligibility criteria during the run-in period OR
- to determine if subject can receive rescue treatment after randomization

During the double-blind randomized treatment period, if the subject meets the criteria for disease worsening as defined in [Section 3.1.2](#) subjects will initiate treatment with etanercept and methotrexate at the same dose they were receiving during the run-in period. Subjects will continue to receive etanercept plus methotrexate for the remaining study visits per [Table 1](#).

### **7.2.8 Subject End of Treatment/Early Termination**

Subjects will complete an end of treatment (EOT) visit at week 48 within a window of  $\pm 7$  days of the target visit date (see [Table 1](#)). Subjects ending the study prior to week 48 will be asked to complete an Early Termination visit.

### **7.2.9 Safety Follow-up/End of Study**

Approximately 30 days, within a window of + 7 days of the target visit date, after the last dose of investigational products, subjects will be contacted by phone by the site staff to collect any serious adverse events (refer to [Section 9](#)).

## **7.3 Description of Study Assessments and Procedures**

Assessment and procedures are further detailed in this section. See [Table 1](#) for required timepoints.

### **7.3.1 Informed Consent**

All subjects or their legally authorized representative must sign and personally date the IEC/IRB approved informed consent before any study-specific procedures are performed. See [Section 11.1](#) for further details.

### **7.3.2 Demographic Data**

Demographic data collection including sex, age, race, and ethnicity will be collected in order to study their possible association with subject safety and treatment effectiveness. Additionally demographic data will be used to study the impact on biomarker variability of the protocol required therapies.

### **7.3.3 Medical History**

The subject's relevant medical and surgical history that started within 5 years or as necessary for chronic co-morbid conditions prior to enrollment through the start of the adverse event reporting period will be collected. Medical history will include information on the subject's concurrent medical conditions. Record all findings on the medical history eCRF. In addition to the medical history above, RA history should date back to the original diagnosis.

#### **7.3.4 Medication History**

The subject's complete history of RA medications will be recorded on the eCRF. This information will include the subject's DMARDs, NSAIDs, corticosteroid, biologics, and investigational medication history. All other medications taken within 6 months prior to screening will be recorded on the eCRF. For RA medications, the following information will be recorded in the eCRF: medication name, indication, dose, unit, route, frequency, and start and stop dates. For all other medications, only the medication name, indication, and start and stop dates will be recorded in the eCRF.

#### **7.3.5 Physical Examination**

The screening physical examination is per standard of care. Physical examination findings at screening should be recorded on the appropriate eCRF (eg, medical history). The physical examination at subsequent study visits will consist of an interim examination to monitor for any changes from the screening physical examination. Any clinically significant changes in physical examination per the Principal Investigator's opinion should be recorded on the adverse events eCRF.

#### **7.3.6 Physical Measurement**

Height in inches/centimeters and weight in pounds/kilograms should be measured without shoes.

#### **7.3.7 Vital Signs**

The following measurements must be performed: systolic and diastolic blood pressure, heart rate, respiratory rate, and temperature. Subject must be in a supine position in a rested and calm state for at least 5 minutes before blood pressure assessments are conducted. If the subject is unable to be in the supine position, the subject should be in the most recumbent position as possible. The position selected for a subject should be the same that is used throughout the study and documented on the vital sign eCRF. The body region used to assess temperature for a subject should remain consistent throughout the study and documented on the vital signs eCRF. If abnormalities are found and they are considered an adverse event, record on the adverse event summary page.

#### **7.3.8 Rheumatoid Arthritis Disease Assessments**

##### **7.3.8.1 Swollen/Tender Joint Counts**

All joint assessments will be performed by an experienced trained joint assessor who has been certified as trained by Amgen and must be identified on the delegation of authority for this responsibility. Each subject should have their joint assessments done

by the same assessor throughout the study when possible and the user identification of the joint assessor is captured in the electronic PRO (ePRO) tablet. If necessary, study visits may be rescheduled within the specified window of  $\pm 7$  days to accommodate when the specific assessor will be available. The score for each joint will be recorded directly into the ePRO tablet which will serve as the source documentation and will not be transposed to the eCRF.

Joints that have been replaced are considered inevaluable. For the screening and baseline joint assessments, distal interphalangeal joints should be evaluated, but should not be included in the total count to determine eligibility.

*Swollen Joint Count Assessments* – A total of 66 joints will be scored for presence or absence of swelling.

*Tender Joint Count Assessments* – A total of 68 joints will be scored for presence or absence of tenderness.

#### **7.3.8.2 Physician Global Assessment of Disease Activity**

The global assessment of the subject's arthritis will be assessed by either the joint assessor or the principal investigator (PI) for the study by completion of a visual analog scale (VAS). The VAS is 100 mm in length with "0" and "No Activity at All" on the left end of the line and "100" and "Worst Activity Imaginable" at the right end of the line. The subject and joint assessor or the PI for the study must complete the global assessments independently from each other.

#### **7.3.8.3 Simplified Disease Activity Index (SDAI)**

The SDAI is the numerical sum of five outcome parameters: tender joint count and swollen joint count based on a 28-joint assessment, patient global assessment of disease activity, physician global assessment of disease activity and C-reactive protein (CRP in mg/dL). SDAI is calculated by the sponsor.

#### **7.3.9 Patient Reported Outcomes**

PRO assessments should be completed first (before other study procedures and administration of study medication) at each visit where they are required.

##### **7.3.9.1 Patient Global Assessment of Joint Pain**

The severity of the subject's joint pain will be assessed by completion of a VAS. The horizontal line is 100 mm in length with "0" and "no pain at all" on the left end of the line and "100" and "worst pain imaginable" on the right end of the line. This questionnaire should take approximately 1 minute to complete.

#### **7.3.9.2 Patient Global Assessment of Disease Activity**

The subject's global assessment of their arthritis disease activity will be assessed by completion of a VAS. The horizontal line is 100 mm in length with "0" and "No RA Activity At All" on the left end of the line and "100" and "Worst RA Activity Imaginable" on the right end of the line. The subject and health care provider must complete the global assessments independently from each other. This questionnaire should take approximately 1 minute to complete.

#### **7.3.9.3 Disability Index of the Health Assessment Questionnaire**

The Disability Index of the Health Assessment Questionnaire (HAQ-DI) will be utilized to assess the subject's physical function or disability according to the subject. The HAQ-DI asks about the degree of difficulty a person has in accomplishing tasks in 8 functional areas (dressing, arising, eating, walking, hygiene, reaching, gripping, and errands and chores). Responses in each functional area are scored from 0 indicating no difficulty to 3 indicating inability to perform a task in that area. The study staff should not clarify any of the questions for the subject. This questionnaire should take approximately 5 minutes to complete.

#### **7.3.9.4 Medical Outcomes Short Form-36 Questionnaire (SF-36)**

The Medical Outcomes Short Form-36 Questionnaire (SF-36) is a 36-item instrument that measures general health status. It includes 8 multi-item scales, each of which assess 1 of the following 8 health concepts: 1) limitations in physical activities because of health problems; 2) limitations in social activities because of physical or emotional problems; 3) limitations in usual role activities because of physical health problems; 4) bodily pain; 5) general mental health (psychological distress and well-being); 6) limitations in usual role activities because of emotional problems; 7) vitality (energy and fatigue); and 8) general health perceptions. The SF-36 assesses the subject's perception of health status over the previous month and takes about 15 minutes to complete.

### **7.4 Laboratory Assessments**

All screening and on-study laboratory samples will be processed and sent to the central laboratory with the exception of erythrocyte sedimentation rate (ESR), urine pregnancy, PPD, and Quantiferon (may be done by central or local laboratory). The central laboratory will be responsible for all screening and on-study serum chemistry, hematology, serum pregnancy, urinalysis, high sensitivity CRP, and any other laboratory tests required. ESR, urine pregnancy and PPD testing, if applicable, will be performed

locally with kits provided by the central laboratory (except PPD). The results of this testing will be maintained in the source documents at the site. Amgen or designee will be responsible for biomarker development and pharmacogenetic assessments, and the central laboratory will ship the samples to Amgen or a specialty laboratory for assay (depending on the assessment). The central laboratory will provide a study manual that outlines handling, labeling, and shipping procedures for all samples. All blood samples will be obtained by venipuncture before investigational product administration. The date and time of sample collection will be recorded in the source documents at the site. Specific analytes for serum chemistry, hematology, urinalysis, and other testing to be conducted on blood and urine samples are listed below (Table 2).

**Table 2. Analyte Listing**

Chemistry	Urinalysis	Hematology	Other Labs
Sodium	Specific gravity	RBC	Serum beta hCG a
Potassium	pH	WBC	Hepatitis B surface antigen and Hepatitis B core antibody b
Chloride	Blood	Absolute neutrophil count	Hepatitis C virus antibody
Bicarbonate	Protein	Hemoglobin	High sensitivity C-reactive protein
Total protein	Glucose	Hematocrit	Tuberculosis Testing c
Albumin	Bilirubin	MCV	Rheumatoid Factor
Calcium	Microscopic (Reflex testing if abnormal)	MCH	Anti-CCP
Adjusted calcium		MCHC	
Magnesium		RDW	
Phosphorus		Platelets	
Glucose		WBC Differential	
BUN or Urea		• Bands/stabs	
Creatinine		• Eosinophils	
Uric acid		• Basophils	
Total bilirubin		• Lymphocytes	
Direct bilirubin		• Neutrophils	
Alkaline phosphatase		• Monocytes	
LDH			
AST (SGOT)			
ALT (SGPT)			

a For all women, unless at least 2 years postmenopausal or history of hysterectomy, bilateral salpingectomy, or bilateral oophorectomy

b At screening, if the subject is positive for hepatitis B core antibody, the confirmatory reflex testing will be performed using HBV DNA PCR.

c Subjects must receive either a PPD test or Quantiferon test at screening. National guidelines should be followed for appropriate tuberculosis screening in the setting of anti-TNF therapy.

#### **7.4.1 Tuberculosis Testing**

National guidelines should be followed for appropriate tuberculosis screening in the setting of anti-TNF therapy.

All subjects must receive either a PPD or Quantiferon test at screening per [Section 4.1.1](#). PPD testing should be performed unless contraindicated.

##### **7.4.1.1 PPD**

The PPD test must be read by a trained healthcare professional 48 to 72 hours after the test is placed. PPD reader must be identified on the delegation of authority for this responsibility.

##### **7.4.1.2 Quantiferon**

If a subject does not receive a PPD test, then a Quantiferon test must be performed per [Section 4.1.1](#). Please refer to the central laboratory manual for instructions on sample collection, processing, and shipping of samples (if applicable).

#### **7.4.2 Erythrocyte Sedimentation Rate**

ESR will be performed locally at each site and the ESR data will be submitted to the central laboratory per the instructions in the study manual provided by the central laboratory. The central laboratory will provide all supplies. The screening and baseline ESR may be performed by any trained staff at the site. Once the subject has been randomized, the ESR may only be performed by a trained individual at the site who does not perform any study assessments with subjects on the study. Staff performing the ESR must be identified on the delegation of authority for this responsibility. The results of the ESR performed after the subject has been randomized must be maintained in a blinded fashion so that it may not be viewed by staff who perform any study assessments with the subjects.

#### **7.4.3 Urine Pregnancy Test**

Urine pregnancy tests will be performed locally at each site. The central laboratory will provide the urine pregnancy tests on visits where required. Urine pregnancy tests must be given prior to dispensing investigational product. If a urine pregnancy test is positive, investigational product must be held; if pregnancy is confirmed, then investigational product must be discontinued.

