### 7.1 Schedule of Assessments

**Table 1. Schedule of Assessments**

	30-day Screening	Open-Label Run-in Period h				Double Blind Treatment Period g						Follow-Up
Weeks		Run-in Visit 1	Run-in visit 2	Run-in visit 3	Run-in ET	0 g	12	24	36	48/ET	Disease Assessment e	Safety (EOS) i
Days	-198 (from Day 1)	-168 (from Day 1)	-84 (from Day 1)	-7 (from Day 1)		Day 1						30
GENERAL & SAFETY ASSESSMENTS												
Informed consent	X											
Part 1 Eligibility Criteria	X											
Part 2 Eligibility Criteria		X	X	X		X						
Medical/Medication history	X											
Concomitant medications		X	X	X	X	X	X	X	X	X	X	
Adverse events		X	X	X	X	X	X	X	X	X	X	
Serious adverse events	X	X	X	X	X	X	X	X	X	X	X	X
Physical examination a	X	X	X	X	X	X	X	X	X	X	X	
Vital signs	X	X	X	X	X	X	X	X	X	X	X	
Weight	X					X				X		
Height	X											
LABORATORY ASSESSMENTS												
Pregnancy test (serum) b	X											
Pregnancy test (urine) b, c		X				X	X	X	X	X		
Tuberculosis testing d	X											
Hematology and chemistry profile	X		X	X				X		X	X	
Rheumatoid Factor and anti CCP antibody						X						
Hepatitis B surface antigen/core antibody & hepatitis C virus antibody j	X											
Erythrocyte Sedimentation Rate	X	X	X	X		X	X	X	X	X	X	
C-reactive Protein	X	X	X	X		X	X	X	X	X	X	
Urinalysis	X			X								
Blood for biomarker analysis						X		X		X		

Footnotes defined on the next page of the table

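### Two dispensing visits, Run-in Visit 2 and the Disease Assessment (rescue) visit, have no scheduled urine pregnancy test, although Protocol 7.4.3 puts the test before dispensing

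*Protocol*

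**What the plan says.** Protocol 7.4.3 gives the rule "Urine pregnancy tests must be given prior to dispensing investigational product". It adds that product is held after a positive test and stopped once pregnancy is confirmed.

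Table 1 of the Protocol sets the visits. The row beginning "Pregnancy test (urine" is marked at Run-in Visit 1 and at Weeks 0, 12, 24, 36 and 48/ET. The row "Methotrexate/placebo for methotrexate dispensation", and the matching etanercept row, are marked at Run-in Visits 1 and 2, at Weeks 0, 12, 24 and 36, and at the Disease Assessment visit. Footnote f explains that last mark: "If subjects meet the criteria for disease worsening then etanercept plus methotrexate will be dispensed at the same dose they were receiving at screening". The serum test is marked at screening only. Footnote b limits testing to women who are neither at least 2 years postmenopausal nor surgically sterile. Footnote c says of anything further: "Additional pregnancy testing may be completed at the discretion of the investigator".

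**The concern.** The rule in 7.4.3 is mandatory and unqualified, while footnote c only permits extra tests. A site that follows Table 1 exactly will dispense at two kinds of visit without a test; a site that follows 7.4.3 literally will test at both. Kits are supplied for visits where a test is required, so an unmarked visit may have none to hand.

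The Protocol itself treats fetal exposure to methotrexate as a hazard (6.9). At Run-in Visit 2, a pregnancy that began after Run-in Visit 1 and is not suspected would not be found by any scheduled test before the next supply is handed over. This is continued exposure: criteria 107 and 108 require at least 6 months on both drugs, and the dose does not change. At an unscheduled rescue visit, women from the etanercept monotherapy arm newly restart active methotrexate; the other two arms never stopped it.

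**Working it through.** **Visits side by side (Protocol Table 1)**

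| Visit | Product dispensed | Urine test |
|---|---|---|
| Run-in Visit 1 | yes | yes |
| Run-in Visit 2 | yes | **no** |
| Run-in Visit 3 | no | no |
| Weeks 0, 12, 24, 36 | yes | yes |
| Week 48/ET | no | yes |
| Disease Assessment | yes, if rescued | **no** |

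Five of the 6 scheduled dispensing visits have a test, or 5 of 7 dispensing columns when Disease Assessment is counted. The two exceptions are the two visits named.

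**Gap between tests in the run-in.** Run-in Visit 1 is 168 days before Day 1, and 168/7 = 24 weeks. For the maximum:
- Run-in Visit 1 to Run-in Visit 3 is 168 − 7 = 161 days.
- Footnote h allows a window of plus or minus 7 "days for all visits after screening", which adds 7.
- Footnote g ("Baseline (Day 1) visit must be scheduled" no more than 7 days from Run-in Visit 3) adds another 7.
- 161 + 7 + 7 = 175 days, or 25 weeks.

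A test at Run-in Visit 2 (Day −84) splits the nominal gap into 84 + 84 days.

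**Age of the last test at an unscheduled rescue.** The Week 12 target is Day 85 (window Days 78 to 92) and the Week 24 target is Day 169 (window Days 162 to 176).
- Earliest Week 12 test to the last day before the Week 24 window opens: 161 − 78 = 83 days.
- On-target Week 12 test to the day before an on-target Week 24 visit: 168 − 85 = 83 days.
- Both extremes, with the Week 24 visit on Day 176 and rescue the day before: 175 − 78 = 97 days.

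The same figures hold for Weeks 24 to 36 and 36 to 48. From Day 1 to the day before the Week 12 window opens it is 77 − 1 = 76 days.

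**Women affected.** The documents do not give the share of women who need testing, so I assume 15% to 50%. The share of women, 2.5/3.5, comes from the prevalence ratio in Protocol 2.1.
- Run-in Visit 2, low: 250 × 2.5/3.5 = 178.6; × 0.15 = about 27.
- Run-in Visit 2, high: 358 × 2.5/3.5 = 255.7; × 0.50 = about 128.
- Restarting methotrexate at rescue: every rescued subject counts as a non-responder (Protocol 10.5.2). At the planned 72% response, at most 100 × (1 − 0.72) = 28 etanercept monotherapy subjects are rescued. 28 × 2.5/3.5 = 20 women; × 0.15 to 0.50 = 3 to 10. Fewer start rescue at unscheduled visits, because rescue at Week 12, 24 or 36 already has a scheduled test.

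**Expected pregnancies.** Protocol 6.9 requires abstinence or contraception with a failure rate below 1% per year under consistent and correct use. Taking 1%:
- Run-in Visit 2: 27 to 128 × 0.01 × 84/365 = about 0.06 to 0.29.
- Rescue: 3 to 10 × 0.01 × 83/365 = about 0.007 to 0.02.

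**The case against.** The best reply is that 7.4.3 only fixes an order: where Table 1 schedules a test, do it before dispensing. Protocol 7.2 says "The procedures performed at each study visit are outlined in" Table 1, and 7.3 refers there for timing. Section 7.4.3 itself speaks of kits for visits where a test is required, and Table 1 has a test at Week 48/ET, where nothing is dispensed. This reading is possible, which is why the point is a conflict and not a breach. But the sentence carries no such limit, and every other scheduled dispensing visit has a test.

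Safeguards also exist: a negative serum test before the run-in (criterion 113), the Run-in Visit 1 urine test, contraception, and stopping on suspicion of pregnancy (6.9). Part 2 eligibility is reviewed at Run-in Visit 2, where criterion 227 brings in the pregnancy exclusion (221). These lower the risk, but without a test none of them detects a new, unsuspected pregnancy at that visit.

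The 12-week interval at rescue is the ordinary interval of the double-blind period, and the expected number of pregnancies is small. Both points stand and limit the size of the problem. They do not remove the 24-week run-in gap or the restart of methotrexate. Study manuals that were not available may say more about these visits.

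Finally, Protocol 7.2.3 describes dispensing at every scheduled run-in visit, while Table 1 has none at Run-in Visit 3. I follow Table 1 there. Read literally, 7.2.3 would add a further untested dispensing visit, though one within 7 days of the Day 1 test.

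**Conclusion.** The concern holds. Run-in Visit 2 and the Disease Assessment visit are the only dispensing columns in Table 1 without a urine test, and 7.4.3 as written exempts neither. The visit counts and intervals come directly from Table 1 and its windows. The numbers of women rest on the assumed 15% to 50% share, on the general prevalence ratio holding in this trial, and on the planned 72% response; the inconsistency depends on none of these.

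The expected harm is small: well under one pregnancy if contraception performs as specified, more if use is imperfect. Day 1 eligibility is protected, because criterion 117 requires a negative test that Table 1 schedules, and the primary analysis is untouched. This is a patient-safety and consistency point that should be fixed because the remedy is cheap. Confidence is moderate, because the ordering-only reading cannot be excluded.

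**What to change.** In Table 1, mark the urine pregnancy test at Run-in Visit 2, and at Disease Assessment visits when rescue product is dispensed, for women not exempt under footnote b. Apply it in all three arms. Since every rescued subject receives methotrexate, testing all of them reveals nothing about the original assignment. Have the central laboratory supply kits for both visits.

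Rewording 7.4.3 alone would remove the inconsistency but leave both gaps. If the sponsor does intend the rule to apply only where Table 1 marks a test, 7.4.3 should say so and justify the two exceptions.

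The cost is two marks in Table 1, about one kit per non-exempt woman at Run-in Visit 2 and one per non-exempt woman rescued at an unscheduled visit, and a few minutes at visits that already take place. The change needs IRB/IEC approval and can go into the next amendment. It needs no extra staff and does not affect sample size or analysis.
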